4.1.5.6 Risk of adverse effects of short-term corticosteroids

Candidates will be screened to ensure there are no contra-indications for transient immune suppression by corticosteroids; in particular, a history of uncontrolled hypertension, diabetes mellitus, tuberculosis, renal impairment, osteoporosis, gastric ulceration, severe affective disorder and immunocompromised status. The possibility of steroid-induced adverse effects will be monitored regularly. In particular, blood pressure and blood glucose will be measured on Baseline, Day 1, Week 1, Week 2 and Week 4, as will renal function and liver function (at baseline and 1 day, 7 days, 2 weeks and 4 weeks and 6 weeks after surgery).

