5.4.1.6 Name and Description of Each Non-Investigational Medicinal Drug (NIMP)

1. Cefuroxime or cefazolin or vancomycin antibiotic given at usual dose at end of surgery (standard dose as prophylaxis for post-operative infection)

2. Betamethasone or dexamethasone given at usual dose at end of surgery (standard dose as prophylaxis for post-operative inflammation)

3. Chloramphenicol 0.5% or ofloxacin (topical antibiotic) 4 times daily for 7 days following ATIMP administration

4. Dexamethasone 0.1% (topical steroid) 4 times daily for 4 weeks, then 2 times daily for a further 2 weeks (weeks 4 to 6) following ATIMP administration

3 and 4 above will be administered to minimise inflammation and protect against infection postoperatively.

5. Omeprazole:

- In adults 20mg per day for 8 weeks
- In children weighing 5 kg to less than 10 kg (11 lb to less than 22 lb): 5 mg taken once per day
- In children weighing 10 kg to less than 20 kg (22 lb to less than 44 lb): 10 mg taken once per day
In children weighing 20 kg (44 lb) or more: 20 mg taken once per day

6. Prednisolone or Prednisone (oral steroid) as prophylaxis against potential intraocular immune responses:

For adults 30 mg daily for one week **prior** to ATIMP administration

Following the ATIMP administration as follows:

- 60 mg daily in week 1
- 40 mg daily in week 2
- 30 mg daily in week 3
- 20 mg daily in week 4
- 15 mg daily in week 5
- 10 mg daily in week 6
- 5 mg daily in week 7
- 2.5 mg daily in week 8

Children will be prescribed a tapering regimen of prednisolone tailored according to age and weight, and in addition intravenous methylprednisolone 30mg/kg on the day of surgery (maximum total no more

MGT003, Gene Therapy Trial for LCA OPTIRPE65

than 1g). A further dose of methylprednisolone may be administered at week 4 in the presence of signs of intraocular inflammation. The detailed treatment regimen is described in a clinical management plan.

All Non Investigational Medicinal Products (NIMPs) are licensed within the EU and US and will be procured from standard hospital stock.

Sites will maintain a system that allows adequate reconstruction of NIMP movements and permits recording of which participants received which NIMPs during the trial, with an evaluation of the compliance where necessary.

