5.4.2.3 Subsequent Assessments

Surgery may be performed, as is conventional for intra-ocular procedures, on a day-case basis. Participants will subsequently be managed as outpatients, though hospital-based accommodation may be used for convenience.

On the first postoperative day a clinical ocular examination will be performed. In particular, visual acuity, intraocular pressure, any postoperative intraocular inflammation and the area of any residual retinal bleb will be documented. Fundus photography and SD-OCT scanning will be performed on the day 1 and subsequent assessments.

A standard post-vitreotomy treatment regimen of topical antibiotic (e.g., chloramphenicol 0.5% qds for 7 days), and corticosteroid (e.g. dexamethasone 0.1% qds for 4 weeks and then bd for a further 2 weeks) will be commenced to minimise inflammation and protect against infection postoperatively. Intraocular pressure of greater than 30 mmHg will be managed using appropriate ocular antihypertensive therapy.

Participants will be maintained on oral prednisolone (or other as appropriate) for 8 weeks following administration of vector suspension as described above (Section 5.4.2.2, Preoperative procedure). The possible development of steroid-induced adverse effects will be monitored regularly. In particular, blood pressure, blood glucose, renal function and liver function will be measured.

Female participants of childbearing potential and male participants with partners of childbearing potential will be advised to use a double barrier method of contraception for 12 months after surgery.

Both safety and efficacy of the ATIMP will be evaluated at various time points up to 6 months after ATIMP delivery. Evaluation will occur primarily by ocular assessments. The nature and schedule (Section 5.6, Study assessments) of these is described below.

Participants will subsequently be invited to enrol in a 5-year follow-up study to determine longer term safety and efficacy.

(i) Clinical assessment of intraocular inflammation

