5.6 Trial Assessments

Table 2: Trial assessments

	Screening	Baseline			ATIMP admin	D1	D3	W1	W2	W4	W6	W9	W12	W24
Flexibility of schedule (\pm days)		- 3 months			Day 0	\pm 0D	\pm 1D	\pm 2D	\pm 4D	\pm 7D	\pm 7D	\pm 7D	\pm 14D	\pm 14D
Visit number	1	2	3	4	5	6	7	8	9	10	11	12	13	14
Informed consent	•													
Physical exam	•													
Medical history	•							•	•	•	•	•	•	•
Eligibility determination	•													
IMP administration					★									
Adverse event review		•	•	•	•	•	•	•	•	•	•	•	•	•
Concomitant medication review	•	•	•	•	•	•	•	•	•	•	•	•	•	•
Genetic screening	•													
Pregnancy test	•				•									
Vital signs (including height and weight) ⁵	•	•				•		•	•	•				
Haematology/Renal Function		•				•		•	•	•	•			
Biochemistry/glucose		•				•		•	•	•	•			
Serology		•								•			•	•
PCR						•				•				
QoL questionnaires (IVI and EQ5D-5L)		•												•
Visual acuity ⁶	•	•	•	•		•	•	•	•	•	•	•	•	•
Contrast sensitivity	•	•	•	•									•	•
Reading speed		•	•	•									•	•
Colour vision		•	•	•									•	•
Octopus perimetry		•	•	•									•	•
Full field Stimulus Testing ⁷		•	•	•									•	•
Microperimetry (mesopic and scotopic)		•	•	•							•		•	•

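### Scheduled blood pressure checks end at week 4 while oral steroid runs to week 8: a minor monitoring gap that one reading at the existing week 6 visit would narrow

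*Combined protocol and SAP*

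**What the plan says.** Section 4.1.5.6 gives two schedules in one sentence. For the first pair of measures, "blood pressure and blood glucose will be measured on Baseline, Day 1, Week 1, Week 2 and Week 4". For the second pair, the list runs on to week 6: "renal function and liver function (at baseline and 1 day, 7 days, 2 weeks and 4 weeks and 6 weeks after surgery".

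Section 5.4.2.3 sets the length of treatment: "Participants will be maintained on oral prednisolone (or other as appropriate) for 8 weeks following administration of vector suspension". It then names the measures for steroid effects, without visit times: "In particular, blood pressure, blood glucose, renal function and liver function will be measured". Section 5.4.1.6 gives the adult regimen: 30 mg/day for one week before surgery, then 60, 40, 30, 20, 15, 10, 5 and 2.5 mg/day in postoperative weeks 1 to 8.

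In Table 2 (section 5.6), the row that begins "Vital signs (including height and weight" is marked at Screening, the first Baseline visit, D1, W1, W2 and W4. The rows "Haematology/Renal Function" and "Biochemistry/glucose" are both marked at the first Baseline visit, D1, W1, W2, W4 and W6.

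**The concern.** The plan itself treats blood pressure as a steroid-safety measure, and by scheduling blood tests at W6 it treats that visit as worth monitoring. The one non-invasive measure of the four is not scheduled there, and no reason is given.

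Raised blood pressure can be symptomless. The adverse event review at W6 and W9 does not itself include a reading, so a rise during the taper could go unseen unless a clinician chose to measure. Only uncontrolled hypertension is excluded (section 5.3.1.3), so someone with controlled hypertension can enter and take the full course. What is at stake is the care of individual participants, not the trial's inference.

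**Working it through.** **Step 1. Which of the four measures is scheduled at W6?**

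| Measure named in 5.4.2.3 | Last time in 4.1.5.6 | Last mark in visible Table 2 | At W6 in either place? |
|---|---|---|---|
| Blood pressure | W4 | W4 (vital signs) | No |
| Glucose | W4 | W6 | Yes, Table 2 only |
| Renal function | W6 | W6 | Yes, both |
| Liver function | W6 | no visible row that names it | Yes, 4.1.5.6 |

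Glucose needs care: 4.1.5.6 on its own ends it at W4 together with blood pressure, and Table 2 is what puts it at W6. None of the four is scheduled after W6.

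**Step 2. How many steroid days follow the last scheduled reading?** Take week k as days 7(k−1)+1 to 7k, so W4 is day 28 and the postoperative course is 8 × 7 = 56 days.

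- After W4: 56 − 28 = 28 days; 28/56 = 50.0%. With the preoperative week, 28/63 = 44.4%.
- Across the W4 window of ±7 days (day 21 to 35): 35 down to 21 days.
- With a W6 reading (day 42): 56 − 42 = 14 days; 14/56 = 25.0%. Across its ±7 days (day 35 to 49): 21 down to 7 days. A W6 visit inside its window therefore always falls within the course.

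**Step 3. How much steroid follows it, in adults?**

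- Preoperative: 30 × 7 = 210 mg.
- Postoperative: (60 + 40 + 30 + 20 + 15 + 10 + 5 + 2.5) × 7 = 1,277.5 mg.
- Total: 1,487.5 mg.
- After W4: (15 + 10 + 5 + 2.5) × 7 = 227.5 mg; 227.5/1,487.5 = 15.3%. As a share of the postoperative course alone, 227.5/1,277.5 = 17.8%.
- Across the W4 window: after day 35, 122.5/1,487.5 = 8.2%; after day 21, 367.5/1,487.5 = 24.7%.
- After W6: (5 + 2.5) × 7 = 52.5 mg; 52.5/1,487.5 = 3.5%.

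These shares describe exposure, not risk. No such figure can be given for children, whose taper is set by age and weight in a separate clinical management plan (5.4.1.6).

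**The case against.** The strongest reply is that the sponsor's schedule is a defensible choice. Readings cover the weeks at 60 to 20 mg/day; afterwards the adult dose is 15 mg/day and falling. Nothing in the protocol requires monitoring up to the last tablet, and 5.4.2.3 does not promise that the four measures share a timetable. Stopping at W6 instead of W4 still leaves weeks 7 and 8 without a reading, so the line is drawn by judgement either way. Other safeguards exist: the exclusion of uncontrolled hypertension, review of history, adverse events and medication at W6 and W9, and freedom to investigate adverse events further. All of this stands, and it is why the point is minor. It does not explain why a visit chosen for the other three measures omits the simplest one.

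A second reply is that the text is incomplete. Footnote 5 on the vital signs row and the later rows of Table 2 are not visible, so an extra reading there cannot be excluded. But 4.1.5.6 gives W4 separately, and would need correcting if Table 2 did go further. That its glucose timing differs from Table 2 is a fair reason not to treat it as beyond error.

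A reader might also infer that children are left unchecked after a strong dose, since "A further dose of methylprednisolone may be administered at week 4 in the presence of signs of intraocular inflammation". The documents do not support that. The dose falls at a visit that already schedules vital signs, and the detailed paediatric regimen is in the clinical management plan, which is not among the documents and may cover it.

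**Conclusion.** The point holds as a minor gap in safety monitoring, at the lowest grade of recommendation. Scheduled blood pressure ends at W4; 28 of 56 postoperative steroid days follow, carrying 15.3% of the adult milligrams (8.2% to 24.7% across the W4 visit window). Of the four named measures, blood pressure alone has no W6 reading in either visible source.

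This assumes that the vital signs row includes blood pressure, that unseen table text adds no later reading, and that visits and doses follow the nominal week count.

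Three stronger readings might be drawn and should not be. The 50% of days is not a measure of risk, because it gives a 2.5 mg day the same weight as a 15 mg day. The revision history might suggest that the W4 limit was left over from a shorter steroid course, but the documents do not say why blood pressure ends there. Nor is dose finding affected: dose-limiting events (4.3.2.1) must be at least possibly related to the vector product, and a blood pressure reading is not itself among them. No estimate or escalation rule changes.

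**What to change.** In Table 2, mark blood pressure (height and weight are not needed) at the existing W6 visit. In 4.1.5.6, add Week 6 for blood pressure and, as an editorial correction, for glucose, so that the sentence agrees with Table 2. A W9 reading is optional: at its earliest (day 63 − 7 = day 56) it coincides with the end of the course, so it serves as an end-of-course check.

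The cost is about one cuff reading per treated participant at a visit already scheduled, or two with W9. For the planned 27 participants that is about 27 or 54 readings, and slightly more if treated participants are replaced, as 5.4.9.1 and 5.6.1 allow. No visit or blood sample is added. Without W9, the nominal stretch with no reading falls from 28 to 14 days and from 15.3% to 3.5% of the adult milligrams; what remains is 5 then 2.5 mg/day, which seems acceptable.

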4.1.5.7 Risks of investigations performed during assessment and follow up

The majority of investigations are non-invasive routine clinical tests and present no significant risk. Venepuncture causes temporary discomfort, occasionally bruising/swelling and rarely infection at the site of puncture.

4.1.5.8 Conclusion on the risk-benefit ratio

In conclusion, the clinical benefit of delivery of the *RPE65* gene to the retinal epithelium was demonstrated in the clinical trial conducted with the first generation product (AAV2/2-hRPE65). Based on the specific modifications to that product (both regulatory elements that control gene expression, and sequences to enhance translation), it is hypothesised that AAV2/5-OPTIRPE65 will produce higher levels of RPE65 protein than AAV2/2-hRPE65, leading to greater improvements in visual function in

patients with LCA2. The investigators judge the scientific value of the trial and potential for individual participants to benefit outweigh the risks associated with the intervention.

4.1.6 Explanation for Choice of Comparators

There is no currently approved treatment for retinal dystrophy caused by mutations in *RPE65*, thus there are no comparators in this study. The contralateral fellow eye will be left untreated to minimize the risk to visual function and may also serve as a control.

4.2 Objectives

4.2.1 Primary Objective

The primary research objective is to assess the safety of a new optimised virus vector for RPE gene replacement in the retina. Safety is defined as an ATIMP related:

- Reduction in visual acuity by 15 ETDRS letters or more
- Severe unresponsive inflammation (defined below)
- Infective endophthalmitis)
- Ocular malignancy
- Grade III or above non-ocular SUSAR (See Section 5.11.3)

Classification of severe unresponsive inflammation will be according to the SUN (standardisation of uveitis nomenclature) Working Group grading system (Am J Ophthalmol. 2005 Sep;140(3):50916.) i.e

- anterior chamber cells 3+ (26-50 cells in a field size of 1mm x 1-mm slit-beam), or
- anterior chamber flare 3+ (marked, iris and lens details hazy) or
- vitreous haze 3+ (Ophthalmology 1985; 92:467-71)

that fail to improve by 2 steps (or to grade 0) during a 6 week period.

4.2.2 Secondary Objective

The secondary research objective is to determine whether a new optimised virus vector for *RPE65* gene replacement in the retina is effective at improving sight in terms of both visual and retinal function, and quality of life.

4.3 Trial Design

4.3.1 Overall Design

This is an open-label phase I/II dose-escalation trial to determine the safety and efficacy of a single subretinal administration of the ATIMP in participants with *RPE65*-related retinal dystrophy.

In the dose escalation phase, up to 18 adult participants will be administered one of 3 different doses of vector in cohorts of 3 participants at a time, using a 3+3 design. Based on toxicity data, the IDMC will

MGT003, Gene Therapy Trial for LCA OPTIRPE65

make a recommendation on the dose to administer to the next cohort of 3 participants. The IDMC may recommend additional participants be treated at a given dose before deciding how to proceed.

Adults are defined as participants aged 16+ in the UK and aged 18+ in the US.

Up to 9 children or adults (aged 3 or older) will then be included once an acceptable safety profile has been established in adults. The IDMC will agree the maximum tolerated dose in adults before recommending administering up to this dose in children.

Safety and efficacy will be assessed by clinical examination and special investigations according to the schedule in section 5.6 of the protocol for 6 months following the intervention.

4.3.1.1 Separate longer term follow up study

Participants will subsequently be invited to enrol in a separate 5-year follow-up study where they will be assessed for safety up to 60 months following ATIMP administration. The duration of long-term follow-up is therefore consistent with the recommendations of the current CHMP Guideline on Follow-up of Patients Administered with Gene Therapy Medicinal Products (EMA/CHMP/GTWP/60436/2007) of 22 October 2009, where it is stated that, for viral vectors without integration, latency or reactivation potential, a brief clinical history and sample testing should be performed pre-treatment, at 3, 6 and 12 months after treatment, and then yearly thereafter for a minimum of 5 years (and, if non-clinical tests or evidence from other clinical trials using identical vectors or modifications of vectors indicate a potential for integration or late re-activation, the monitoring should be extended to continue yearly after those 5 years until data indicate that there is no longer any risk to be followed). Further, although the FDA Guidance for Industry: Gene Therapy Clinical Trials – Observing Subjects for Delayed Adverse Events (November 2006) recommends a standard 15-year period of follow-up, it is also noted that a shorter period of follow up may be possible if the vector does not integrate and has no potential for latency and reactivation. The follow up study will be a non-intervention study designed to collect data on longer term safety and efficacy at the equivalent of 9, 12, 18, 24, 36, 48 and 60 months following ATIMP administration; as such, participants in both studies will be followed up more frequently than recommended in the guidance, as additional assessments following ATIMP administration are included in the initial study (at weeks 1, 2, 4, 6 and 9) and in the long-term follow up study (at months 9 and 18). The follow up study will be supported by a different source of funding, will have a separate protocol, participant information and consent processes, and will be submitted for separate ethical review. Participants in the current study will be encouraged to join the follow up study as part of their ongoing clinical review, but there will be no obligation on their part to do so. It is acknowledged that despite encouragement participants may choose not to participate in the long-term follow-up study; however, in this motivated population, where individuals are closely and regularly monitored by their specialist, this number is expected to be very small. Moreover, we anticipate that participants are more likely to join a long-term study at 6 months than at 2 years following intervention.

4.3.2 IMP administration Review and Dose Escalation Criteria and Process

Up to 18 adult participants (as defined in Section 4.3.1) will be administered 1 of 3 doses according to the dose-escalation criteria:

MGT003, Gene Therapy Trial for LCA OPTIRPE65

- | | |
|----------------------|-----------------------------------|
| 1) low dose | 1mL at 1.0×10^{11} vg/mL |
| 2) intermediate dose | 1mL at 3.0×10^{11} vg/mL |
| 3) high dose | 1mL at 1.0×10^{12} vg/mL |

Once a maximal tolerated dose is established, up to a further 9 participants aged 3 or above will continue to be administered vector up to the highest dose observed to be well tolerated in adults.

4.3.2.1 Dose escalation criteria and Dose Limiting Events

Dose escalation will be undertaken in adults, based on an escalation rule around Dose-Limiting Events (DLEs). An IDMC will review data from a minimum of 9 weeks of follow up from each cohort of 3 participants, before recommending the next dose to be assessed in a further cohort of participants.

A DLE is defined as any of the below occurring during the 9 weeks following administration, at least possibly related to the ATIMP, not surgery alone:

- Reduction in visual acuity by 15 ETDRS letters or more
- Severe unresponsive inflammation
- Infective endophthalmitis
- Ocular malignancy or
- Grade III or above non-ocular SUSAR (see section 5.11.3)

Severe unresponsive inflammation will be defined according to the Standardisation of Uveitis Nomenclature (SUN) Working Group grading system (Jabs *et Al.* 2005) i.e.

- anterior chamber cells 3+ (26-50 cells in a field size of 1mm x 1-mm slit-beam), or
- anterior chamber flare 3+ (marked, iris and lens details hazy), or
- vitreous haze 3+ (Ophthalmology 1985; 92:467-71)

that fails to improve by 2 steps (or to grade 0) during a 9-week period.

Review of safety data will be undertaken by the IDMC prior to each dose escalation. Children will be included at up to the highest safe vector dose recommended by the IDMC, once a safety profile has been established in adult participants.

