4.3.2.2 Dosing process

4.3.2.2.1 Cohort 1

Vector will first be administered at the lowest dose to 1 adult participant only. This participant will be monitored for signs of toxicity for a period of 9 weeks. If there is no DLE as defined above after a minimum of 9 weeks, vector will continue to be administered at the same dose to 2 further adult participants. In the event of a DLE in the first adult in the cohort, a discussion will be held with the IDMC to agree a plan of action for administering the ATIMP to further adults. The IDMC will review the data collected on this cohort of participants up to 9 weeks following vector administration to the 3rd participant.

4.3.2.2.2 Cohort 2

In the event that there is no DLE in any participant, the IDMC will recommend administering vector at the intermediate dose level to a single adult participant. If there is no dose-limiting toxicity after a minimum of 9 weeks, vector will continue to be administered at the same dose to 2 further adult participants. In the event of a DLE in the first adult in the cohort, a discussion will be held with the IDMC to agree a plan of action for administering the ATIMP to further adults. The IDMC will again review the data available on this next cohort of adult participants up to 9 weeks following vector administration to the 3rd participant.

4.3.2.2.3 Cohort 3

In the event that there is no DLE in any participant, the IDMC will recommend administering vector at the highest dose level to a single adult participant. If there is no DLE after a minimum of 9 weeks, vector will be administered at the same dose to 2 further adult participants. In the event of a DLE in the first adult in the cohort, a discussion will be held with the IDMC to agree a plan of action for administering the ATIMP to further adults.

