6.13 Publication Policy

6.13.1 Trial Results

All proposed scientific publications will be discussed with the Sponsor prior to publication. Since this is an exploratory, open-label, Phase I/II trial, progress and significant findings may be presented at scientific forums/meetings and/or published during the course of the trial.

The results of the trial will be disseminated regardless of the direction of effect.

7 Ancillary Studies

There are no currently planned ancillary studies. Any future ancillary studies will be subject to separate funding, and will be submitted for ethical and regulatory review as appropriate.

8 Revision History

Protocol Version and Date	Reason for Amendment
Protocol V1.1 dated 28.01.2016	Clarify safety reporting procedures as requested by MHRA
Protocol V2 dated 6 th June 2016	Further clarification of safety reporting procedures as requested by the MHRA. Updated inclusion/exclusion criteria as requested by the US FDA. Enhanced description of the method of measuring the primary objective and outcome Enhanced description of the dose limiting criteria

MGT003, Gene Therapy Trial for LCA OPTIRPE65

	
Minor modification to wording and language to correct typographical errors and ensure consistency throughout
 
Change in name of funder from Athena Vision Ltd. to MeiraGTx UK Ltd.

Protocol V3 dated 2 nd August 2016	
Visual acuity assessments at day 1 and day 3 post-treatment had been erroneously omitted from V2. These were replaced.
 
UCL CCTU Clinical Project Manager was replaced and details updated.

Protocol V4 dated 10 February 2017	
To reflect the change in sponsor from UCL to MeiraGTx UK II Ltd.
 
Minor modification to wording and language to correct typographical errors and ensure consistency throughout
 
To clarify the DLE and safety definitions
 
To clarify the primary objective and outcome measures
 
To describe the outsourcing of data management, pharmacovigilance and clinical monitoring to CROs

Protocol V5 dated 12 April 2017	
To extend the course of post-surgery prophylactic steroids from 4 weeks to 8 weeks. Consequently, the duration for considering dose limiting events has been extended from 6 weeks to 9 weeks to cover the period of steroid administration and one additional week and other minor clarifications

Protocol V6 dated 21 August 2017	
To update the prophylactic steroid regimen in children, and clarify safety reporting and safety dose for children

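### The week-9 visit may be held as early as day 56, so a release at day 63 can rest on an examination short of the plan's own 9-week minimum

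*Combined protocol and SAP*

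**What the plan says.** Four parts of the protocol bear on this.

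- **Minimum follow-up.** Section 4.3.2.1 states: "An IDMC will review data from a minimum of 9 weeks of follow up from each cohort of 3 participants". Section 4.3.2.2 applies the same length to the first participant at each dose, who must be free of DLEs before two more adults are treated: "If there is no DLE as defined above after a minimum of 9 weeks". For the first cohort it adds: "The IDMC will review the data collected on this cohort of participants up to 9 weeks following vector administration to the 3rd participant". Section 4.3.2.2.5 repeats the 9-week wait for the first child.
- **DLE period.** Section 4.3.2.1: "A DLE is defined as any of the below occurring during the 9 weeks following administration". The components include a loss of 15 or more ETDRS letters.
- **Visit schedule.** Table 2 in section 5.6 has post-dose columns "D1 D3 W1 W2 W4 W6 W9 W12 W24". Its row "Flexibility of schedule" gives plus or minus 7 days at W9 and plus or minus 14 days at W12. Visual acuity is marked at both visits.
- **Why 9 weeks.** Section 5.4.2.3: "Participants will be maintained on oral prednisolone (or other as appropriate) for 8 weeks following administration of vector suspension". The entry for protocol version 5 in section 8 explains that the DLE period was lengthened "to cover the period of steroid administration and one additional week". It is cited here only as the reason for the current 9-week rule.

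**The concern.** A minimum and a symmetric window do not fit together. The text sets a floor of 9 weeks, while the schedule lets the visit that supplies the closing data take place up to a week below it, without any protocol deviation. The ninth week was added so that observation would run past the end of the oral steroid course. If the visit is early, some or all of that week has no scheduled examination before the next participants or the next dose can be released.

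Cohorts have three participants, so one event matters. At the low and intermediate doses Table 1 reads 0/3 as escalate and 1/3 as stay at the dose and expand. At the high dose 0/3 identifies the MTD, while 1/3 calls for three more participants.

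**Working it through.** **Inputs.** Minimum follow-up and DLE period: 9 weeks (4.3.2.1, 4.3.2.2). Oral steroid after dosing: 8 weeks (5.4.2.3; the adult taper in 5.4.1.6 ends with week 8). Windows: W6 ± 7, W9 ± 7 and W12 ± 14 days (Table 2).

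**The plan's own figure.** 8 weeks of steroid + 1 additional week = 9 weeks = 9 × 7 = 63 days. It reproduces.

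**Permitted visit days** (nominal day ± window):

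| Visit | Nominal day | Earliest | Latest |
|---|---|---|---|
| W6 | 42 | 35 | 49 |
| W9 | 63 | 56 | 70 |
| W12 | 84 | 70 | 98 |

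**Shortfall.** The W9 window has 70 − 56 + 1 = 15 days. Days 56 to 62 are below 63, which is 7 of 15. For a visit on day d in that range, the interval left unexamined at day 63 is 63 − d, from 1 day (d = 62) to 7 days (d = 56).

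**Next scheduled examination.** After a day-56 visit, W12 follows 70 − 56 = 14 to 98 − 56 = 42 days later. No scheduled visit need fall between day 56 and a release at day 63.

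**Position relative to the steroid course.** The protocol does not say whether week 1 starts on the day of dosing or the day after, so both counts are shown.

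| Day count | Last dose | Whole steroid-free days before a day-56 visit | Before a day-63 visit |
|---|---|---|---|
| Week 1 = days 0–6 | day 55 | 0 | 63 − 55 − 1 = 7 |
| Week 1 = days 1–7 | day 56 | 0 | 63 − 56 − 1 = 6 |

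On either count a day-56 visit examines none of the additional week, and a day-63 visit examines all or nearly all of it.

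**Who is affected.** Participants 2 and 3 are dosed at least 63 days after the first, and cohort data run to 63 days after the third. By then the first participant is at day 63 + 63 = 126 or later, beyond the latest W12 day of 98. The gap therefore bears on the release that follows the first participant, and on participants 2 and 3 at cohort review.

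**The case against.** The strongest reply is that the plan requires 9 weeks of follow-up and does not say that an examination must close it. Release before day 63 is barred whenever the visit is held. Between visits, adverse events are recorded (5.11.3.6.1), serious events are notified within 24 hours (5.11.3.5), safety events are reviewed promptly (5.11.3.2) and participants have a 24-hour hotline (5.8.2). The IDMC reviews safety before each escalation and may ask for more participants at a dose. This stands in part: an early visit does not leave the trial unobserved. It does not close the gap, because a 15-letter loss is established by chart testing, and the treated eye is expected to be the poorer-seeing one, where a change may go unreported. Nothing in the available text requires an examination on or after day 63.

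A second reply is that the text may be incomplete. Table 2 breaks off before its remaining rows and footnotes, and IDMC procedures are in a charter that was not available. A restriction on the W9 window may exist in either place.

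Three stronger readings are tempting, and the documents do not support them.

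- *That escalation can rest on an eye never examined off oral steroid.* Only a day-56 visit could coincide with the last dose, and it does not if week 1 starts on day 0. Visits on days 57 to 62 follow the last dose on either count.
- *That severe inflammation after steroid withdrawal would be lost from the DLE count.* Section 4.3.2.1 counts inflammation only if it fails to improve over a 9-week period. Inflammation first appearing in week 9 cannot meet that by day 63, whenever the visit is held.
- *That the late half of the window also understates the count.* Visits on days 64 to 70 satisfy the minimum. The definition turns on when an event occurs, not when it is found, so an event found on day 66 may still be dated to week 9.

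**Conclusion.** The inconsistency is real and narrow. The 9-week minimum and the W9 window disagree on 7 of 15 permitted days, and a release at day 63 can rest on an examination 1 to 7 days short of the minimum. The exposure is to DLE components that can arise and be detected within that week, acuity loss being the clearest. It applies mainly to release after the first participant and to the later participants of a cohort.

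The 7 of 15 counts permitted days and is not a probability. The documents give neither the distribution of visit dates nor an event rate for week 9, so the chance of a wrong escalation cannot be calculated, and a systematic undercount of DLEs is not shown.

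The conclusion assumes that W9 is in practice the last examination before release, that release may occur as early as day 63, and that no unseen footnote or charter rule narrows the window.

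**What to change.** Reconcile the W9 window in Table 2 with the minimum in 4.3.2.1, 4.3.2.2 and 4.3.2.2.5, for example by making it minus 0, plus 7 days (days 63 to 70). State in 4.3.2.2 that the data supporting release of further participants, or of the next dose, include the completed W9 examination, and carry the same sentence into 4.3.2.2.5. If a footnote or the IDMC charter already says this, a cross-reference is enough.

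As an optional clarification, state in 4.3.2.1, 5.5.1 and 5.10.4.2 how an event first found at a W9 visit after day 63 is dated for the DLE count.

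The cost is an amended window and one or two sentences, with no added visit or procedure. A release decision may come up to 7 days later (70 − 63). No change to any dose or steroid rule is proposed.
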